**LIST OF ABBREVIATIONS (EXAMPLES)**

AE	Adverse Event
ALT	Alanine Aminotransferase
ALC	Absolute Lymphocyte Count
ASCO	American Society of Clinical Oncology
AST	Aspartate Aminotransferase
BUN	Blood Urea Nitrogen
CBC	Complete Blood Count
CEDM	Contrast enhanced digital mammography
CMP	Comprehensive Metabolic Panel
CR	Complete Response
CT	Computed Tomography
CTCAE	Common Terminology Criteria for Adverse Events
DLT	Dose Limiting Toxicity
DOT	Disease Oriented Team
DSMB	Data and Safety Monitoring Board
ECOG	Eastern Cooperative Oncology Group
FDA	Food and Drug Administration
GCP	Good Clinical Practice
H&P	History & Physical Exam
HRPP	Human Research Protections Program
IDE	Investigational Device Exemption
IHC	Immunohistochemistry
IND	Investigational New Drug
IV (or iv)	Intravenously
MRI	Magnetic Resonance Imaging
MTD	Maximum Tolerated Dose
NCI	National Cancer Institute
ORR	Overall Response Rate
OS	Overall Survival
PBMCs	Peripheral Blood Mononuclear Cells
pCR	Pathologic Complete Response
PD	Progressive Disease
PET	Positron Emission Tomography
PFS	Progression Free Survival
p.o.	peros/by mouth/orally
PR	Partial Response
RCB	Residual Cancer Burden
RECIST	Response Evaluation Criteria in Solid Tumors
SAE	Serious Adverse Event
SCCC	Simmons Comprehensive Cancer Center
SD	Stable Disease

[figure not shown]
Study Number – Insert PRMC Assigned SCCC- Protocol Number (found on the PRMC approval letter)

---

SGOT	Serum Glutamic Oxaloacetic Transaminase
SPGT	Serum Glutamic Pyruvic Transaminase
WBC	White Blood Cells

---

**STUDY SCHEMA**

Study Number – Insert PRMC Assigned SCCC- Protocol Number (found on the PRMC approval letter)

**STUDY SUMMARY**

Title	Performance of contrast-enhanced spectral mammography to assess neoadjuvant therapy response
Short Title	Contrast-enhanced mammography Assessment of Breast Cancer Neoadjuvant Therapy response
Protocol Number	The standard protocol number used to identify this study
Phase	III
Methodology	Prospective, Single Arm, Unblinded
Study Duration	24 months
Study Center(s)	Single-Center, UTSW Breast Center & Parkland Moody Center for Breast Health
Objectives	
Primary Objectives
 
 
1. To investigate the diagnostic accuracy of Contrast Enhanced Spectral Mammography (CEDM) in predicting early neoadjuvant therapy response and pCR compared to mammography.
 
2. To investigate the correlation accuracy of CEDM pre-operative lesion size and final pathological size, compared to mammography.
 

Number of Subjects	100
Diagnosis and Main Inclusion Criteria	
 
1. 18 years and older male or female patients
 
2. Ipsilateral intact biopsy-proven breast cancer clinical T1-T4 (by imaging)
 
3. Available mammography and ultrasound imaging of the existing index cancer, with orthogonal measurements
 
4. Prior history of ipsilateral or contralateral breast cancer, presenting with a new primary or recurrent disease.
 
5. Patients who were determined to be candidates for either neoadjuvant chemotherapy or neoadjuvant endocrine therapy by the treating physician.
 
6. Women of child-bearing potential and men must agree to use adequate contraception (hormonal or barrier method of birth control; abstinence) prior to study entry, for the duration of study participation, and for days following completion of study participation. Should a woman become pregnant or suspect she is pregnant while participating in this study, she should inform her treating physician immediately.
 

Study Product(s), Dose, Route, Regimen	Contrast-Enhanced Digital Mammography
Duration of administration	N/A
Reference therapy	
Statistical Methodology	Descriptive Statistics will be produced. Spearman rank correlation will be used to measure the agreement between final pathologic and imaging tumor size data. ROC analysis will be used to assess the diagnostic performance of CEDM.

## 1.0 BACKGROUND AND RATIONALE

### 1.1 Disease Background

The use of neoadjuvant systemic therapy in the treatment of breast cancer patients is increasing beyond the scope of locally advanced disease. Imaging provides important information in assessing response to therapy as a complement to conventional tumor measurements via physical examination. Tumor response to neoadjuvant therapy can also provide prognostic information. The attainment of pathologic complete response (pCR) after completion of neoadjuvant therapy and surgical resection is associated with improved disease-free survival (1-3). This correlation is especially strong for Triple-receptor negative (ER, PR negative and HER-2 non amplified), and HER-2 positive breast cancer. Studies of neoadjuvant therapy have used a variety of methods for assessing tumor response. Currently, there are no established clinical practice guidelines for how best to assess tumor response to neoadjuvant therapy. Typically, patients undergo conventional breast imaging (mammography and ultrasonography [US]) and physical examination, and dynamic contrast-enhanced breast MRI (DCR-MRI) in selected cases.

### 1.2 Study Agent(s)/Therapy(ies) Background and Associated Known Toxicities

Studies of neoadjuvant therapy have used a variety of methods for assessing breast cancer response to neoadjuvant therapy. Physical measurement of tumor size with calipers is typically performed prior to each chemotherapy cycle or monthly if neoadjuvant endocrine therapy is used (4). The accuracy of clinical breast examination for determining pCR in patients with locally advanced breast cancer after neoadjuvant hormonal or chemotherapy is 57%, which is inferior to mammography (74%) and US (79%) (5,6). Mammography has been shown to be more sensitive than physical examination for detecting presence of residual tumor after therapy but is less specific and may underestimate the degree of treatment response (7,8). The mammographic lesion type, such as architectural distortion, and margin impact its accuracy for size measurement, with decreased accuracy when margins are indistinct or spiculated and due to masking from adjacent normal tissue (9). Additional challenges with mammography include the presence of microcalcifications, which do not correlate with presence of viable tumor (10-12). US has been shown to be a better predictor for pathologic tumor size than mammography after treatment with neoadjuvant therapy (13-15). The sensitivity and specificity of mammography in predicting pathologic complete response were 54.2% and 86.3%, respectively. The sensitivity and specificity of breast ultrasound in predicting pathologic complete response were 45.8% and 93.8%, respectively. The best method for predicting complete pathologic response (pCR) appears to be the combination of mammography with US (80% likelihood when findings of both modalities are negative) (14,16). **Standard imaging methods used to monitor response to neoadjuvant therapy are summarized in Table 1.**

**Table 1. Standard imaging methods used to monitor response to neoadjuvant therapy**

Table 1			
Current Breast Imaging Utilized Prior to Neoadjuvant Therapy			
Variable	Mammography*	Breast US†	Breast MR Imaging‡
Ipsilateral breast	Extent of disease evaluation: full-field craniocaudal, full-field mediolateral oblique, full-field mediolateral/ lateromedial plus spot compression craniocaudal, spot compression mediolateral/ lateromedial	Extent of disease evaluation targeted to index lesion	Extent of disease evaluation: pectoralis/ chest wall invasion
Contralateral breast	Screening: full-field craniocaudal, full-field mediolateral oblique	Not typically performed	Screening
Lymph nodes§	Lymphadenopathy evaluation: axillary (incomplete)	Lymphadenopathy evaluation: axillary	Lymphadenopathy evaluation: axillary, internal mammary

\* Digital breast tomosynthesis may be utilized as part of the diagnostic evaluation. Substitute spot compression views with magnification craniocaudal and mediolateral/lateromedial views if associated microcalcifications.

† Whole-breast US may be performed for patients unable to undergo magnetic resonance (MR) imaging, particular for patients with mammographically dense breasts. However, the relatively high rate of false-positive findings limits recommendation of this approach.

‡ Utilization of breast MR imaging may vary with clinical practices due to surgeon and/or oncologist preferences.

§ Fluorine 18 fluorodeoxyglucose (FDG) positron emission tomography (PET)/computed tomography (CT) imaging may be helpful for evaluating regional nodal sites of disease (axilla, internal mammary, and supraclavicular) for locally advanced breast cancer, especially in patients presenting with more advanced axillary disease.

**Table 2. Meta-analyses depicting MRI sensitivity in achieving pCR (from Fowler et al Radiology 2017 Nov)**

Table 2							
Meta-Analyses of Breast MR imaging for Evaluation of Neoadjuvant Therapy Response							
Meta-Analysis	No. of Studies	No. of Patients	Pooled Sensitivity (%)	Pooled Specificity (%)	Likelihood Ratio Positive	Likelihood Ratio Negative	Diagnostic Odds Ratio
Yuan et al 2010 (34)	25	1212	63 (56–70)*	91 (89–92)*	Not reported	Not reported	17.05 (10.59–27.19)
Wu et al 2012 (35)	30	1496	68 (57–77)*	91 (87–94)*	7.48 (5.29–10.57)	0.36 (0.27–0.48)	20.98 (13.24–33.24)
Marinovich et al 2013 (36)	44	2050	83–87†	54–83†	Not reported	Not reported	Not reported
Sheikbahaei et al 2016 (37)	10	492	88 (76–95)	55 (41–68)	Not reported	Not reported	Not reported

Note.—Data in parentheses are the range.

\* Sensitivity defined as ability to correctly identify patients achieving pCR after preoperative therapy. Specificity defined as ability to correctly identify nonpCR after preoperative therapy.

† Sensitivity defined as ability to correctly identify presence of residual tumor after preoperative therapy in patients with nonpCR. Specificity defined as ability to correctly identify absence of residual tumor after preoperative therapy in patients with pCR.

DCE-breast MRI sensitivity and specificity in predicting pCR ranges from 63-88% and 55-91%, heavily depending on the imaging cut off criteria used to define imaging complete response on MRI interpretation. As demonstrated by a recent meta-analysis (Table 2) MRI can significantly underestimate residual disease. This is likely due in part because initial tumor enhancement and visibility on MRI peaks at 2 minutes, however with chemotherapy contrast delivery to the tumor may be significantly delayed due to the disruption of neovasculature.

### 1.3 Other Agents

Contrast Enhanced Digital Mammography (CEDM) is a novel imaging technique, which allows digital mammography to be used with contrast enhancement to depict cancers that would otherwise be occult on standard unenhanced mammography. CEDM is performed with and without i.v. iodine contrast, using the dual energy subtraction technique (20-25). Compared with mammography and US, CEDM improves the sensitivity for breast cancer detection without decreasing specificity (20,21). CEDM digital detector has higher spatial resolution than MRI (i.e. typically pixel sizes 100  $\mu$ m and 1 mm, respectively), revealing

Study Number – Insert PRMC Assigned SCCC- Protocol Number (found on the PRMC approval letter)

---

details that are approximately 10 times better. In contrast to the rapid washout in MRI, enhancement on CEDM in fact persists for at least 10 min after contrast agent infusion. Today CEDM is available commercially for clinical use. It is estimated that over 200,000 CEDM examinations have been performed to date in both research and clinical settings. CEDM costs significantly less compared to MRI. (26). Furthermore, longer time delays between contrast injection and CEDM exposure could result in stronger enhancement and hence better visibility compared to MRI, especially given the much higher spatial resolution of digital mammography. It is unknown whether CEDM can improve the sensitivity of mammography in the early assessment of neoadjuvant therapy response. We hypothesize that CEDM is superior to mammography and ultrasound in assessing early response, and pre-surgical residual cancer after neoadjuvant therapy, and when performed, non-inferior to MRI in assessing the residual disease using the metrics of pCR and RCB.

#### **1.4 Rationale**

The use of neoadjuvant systemic therapy in the treatment of breast cancer patients is increasing beyond the scope of locally advanced disease. Imaging provides important information in assessing response to therapy as a complement to conventional tumor measurements via physical examination. Tumor response to neoadjuvant therapy can also provide prognostic information. The attainment of pathologic complete response (pCR) after completion of neoadjuvant therapy and surgical resection is associated with improved disease-free survival (1-3). This correlation is especially strong for Triple-receptor negative (ER, PR negative and HER-2 non amplified), and HER-2 positive breast cancer. Studies of neoadjuvant therapy have used a variety of methods for assessing tumor response. Currently, there are no established clinical practice guidelines for how best to assess tumor response to neoadjuvant therapy. Typically, patients undergo conventional breast imaging (mammography and ultrasonography [US]) and physical examination, and dynamic contrast-enhanced breast MRI (DCR-MRI) in selected cases.

### **2.0 STUDY OBJECTIVES**

#### **2.1 Primary Objectives**

- 2.1.1** To investigate the diagnostic accuracy of Contrast Enhanced Spectral Mammography (CEDM) in predicting early neoadjuvant therapy response and pCR.

#### **2.2 Secondary Objectives**

- 2.2.1** To investigate the correlation of CEDM pre-operative lesion size and final pathological size.
- 2.3.1** **2.2.2** To determine additional sites of disease in the ipsilateral or contralateral breast identified by CEDM.

#### **2.3 Exploratory Objectives**

**To determine the optimal post neoadjuvant therapy CEDM timing which helps demonstrate the residual disease extent.**

- 2.3.2.** To identify any patient preference differences between CEDM and breast MRI

## 2.4 Endpoints

2.4.1 Primary: Diagnostic performance (sensitivity and specificity) measured as area under the curve (AUC) in the response assessment by varying metrics including pCR and RCB classification.

2.4.2 Secondary: Correlative statistic for CEDM lesion sizing vs pathologic lesions sizing, frequency of finding additional sites of disease in ipsilateral or contralateral breasts by CEDM and number of such new lesions.

2.4.3 Exploratory: AUC of CEDM using varying time points for CEDM, survey scores for patient experience with CEDM

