##### 3.2.6

Eligible patients will be imaged at baseline (before initiation of neoadjuvant chemotherapy or endocrine therapy), early (2-4 cycles of neoadjuvant therapy) and late (after completion of neoadjuvant chemotherapy or endocrine therapy) timepoints with mammography. CEDM will be done within 2 weeks of the specified timepoint. Three dimensional orthogonal measurements will be obtained in all timepoints. Additional sites of disease in the ipsilateral or contralateral breast identified by CEDM will be recorded and reported. ACR BI-RADS MRI lexicon will be used for reporting.

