**5.1.2** **Medical history, and reviewing subject eligibility criteria previous and concomitant medications**

#### **Informed Consent**

#### **5.2 Procedures During CEDM**

CEDM will be performed using UTSW Imaging Protocol (**attached, Appendix A**), including monitoring for immediate contrast reactions.

Discussion of additional findings: All breast imaging findings are routinely discussed with the patient by the radiologist immediately after imaging in our clinical practice. Additional findings identified on CEDM will be addressed similar to additional disease noted on ultrasound or breast MRI per standard of care.

Study Number – Insert PRMC Assigned SCCC- Protocol Number (found on the PRMC approval letter)

---

Survey of patient experience with CEDM and other pre-operative imaging such as MRI will be collected after CEDM is performed, optimally at pre-operative time point (Appendix B).

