**5.3 Follow-up Procedures**

Patients' medical records will be followed 30 days after completion of definitive surgery to collect final pathology outcomes, or if they develop progressive disease.

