## **6.3 Pathology**

Final histopathology for correlation will include the size of residual tumor (ypT), tumor cellularity (%) and amount of DCIS (%). Per AJCC8th edition [Amin MB, Edge SB, Greene FL, et al, eds. AJCC Cancer Staging Manual. 8th ed. New York: Springer; 2017] (ypT) is based on the largest continuous focus of residual invasive cancer, if present. Treatment-related fibrosis adjacent to residual invasive carcinoma or between foci of residual cancer is not included in the ypT maximum dimension. When multiple foci of residual tumor are present, the (m) modifier is included.

In addition, we will record ki67 index pre and post therapy and its potential correlation with the degree of tumor response seen on CEDM.

The agreement between pre-operative CEDM measurements and mammography in categorizing tumor response RCB0-I/ RCBII/RCBIII will be assessed using weighed kappa.

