### **8.3 Data Analyses**

Descriptive statistics will be produced for all patients; frequencies and percentages for categorical measures and means, medians, standard deviations, and ranges for continuous measures. The number of cancer foci identified by each imaging modality will be compared. Tumors will be categorized according to immunohistochemical approximated molecular profiles (Luminal A, Luminal B, Triple-negative and HER-2 amplified). Additional exploratory analyses will be performed as needed.

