#### **1. Sensitivity of CEDM versus mammography**

Histopathological assessment will be used as the reference standard.

For categorical measurements of tumor response (CR/PR/SD/PD or RCB0-I /RCB II /RCB III):

1. Sensitivities and specificities in predicting pCR (or RCB0) will be calculated for CEDM and mammography respectively.
2. The agreement between CEDM and mammography in categorizing tumor response (CR/PR/SD/PD or RCB0-I/ RCBII/RCBIII) will be assessed using weighed kappa.

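### Additional disease sites and cancer foci are counted by imaging alone, so false-positive findings can be reported as extra cancer

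*Combined protocol and SAP*

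**What the plan says.** Three places define the additional-sites endpoint, all by what CEDM shows:

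- Objective, section 2.2: "To determine additional sites of disease in the ipsilateral or contralateral breast identified by CEDM".
- Endpoint, section 2.4.2: "frequency of finding additional sites of disease in ipsilateral or contralateral breasts by CEDM and number of such new lesions".
- Recording rule, section 4.0 (paragraph numbered 3.2.6): "Additional sites of disease in the ipsilateral or contralateral breast identified by CEDM will be recorded and reported".

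Section 8.3 then widens the count to all modalities: "The number of cancer foci identified by each imaging modality will be compared".

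Four other provisions touch on confirmation:

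- Section 8.3, item 1, on the sensitivity of CEDM versus mammography: "Histopathological assessment will be used as the reference standard". The item goes on to tumor response and pCR.
- Section 6.3: "Final histopathology for correlation will include the size of residual tumor (ypT), tumor cellularity (%) and amount of DCIS".
- Section 5.2, on handling: "Additional findings identified on CEDM will be addressed similar to additional disease noted on ultrasound or breast MRI per standard of care".
- Section 5.3: "medical records will be followed 30 days after completion of definitive surgery to collect final pathology outcomes".

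**The concern.** A count of sites labelled disease or cancer is read as a count of cancers. If a site qualifies because an image shows it, benign enhancement counts the same as an additional tumor. The frequency then mixes added cancer yield with added false alarms, and the comparison in section 8.3 credits whichever modality marks more.

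This matters because section 8.2 says the results should help design a larger multi-institutional study comparing modalities. The protocol also takes both issues seriously elsewhere. Section 3.1 requires the index cancer to be proven by biopsy, and a footnote to Table 1 gives false positives as the reason for not favoring whole-breast ultrasound. For additional sites on CEDM, no false-positive count or PPV is planned.

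**Working it through.** **1. Is there a confirmation rule anywhere?**

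- Sections 2.2, 2.4.2 and 4.0 rest on CEDM identification. None mentions biopsy, surgical pathology or follow-up as proof.
- The foci comparison in section 8.3 stands before item 1 and has no reference standard. The histopathology sentence belongs to item 1, which concerns response and pCR.
- Section 6.3 collects residual tumor size, cellularity and DCIS after therapy, with a modifier for multiple foci. It does not match pathology to each imaging site.
- Section 5.2 sends findings to routine handling. It mandates no tissue diagnosis and feeds no result back into the endpoint.
- The BI-RADS MRI lexicon in section 4.0 standardizes description. No assessment category is set as the threshold for disease.

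**2. The plan's own figures (section 8.2).** With 100 patients and 40% pCR there are 40 with pCR and 60 without. The maximum 95% half-width for a proportion is 1.96·√(0.25/n) + 1/(2n).

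- Sensitivity, n = 40: 0.1549 + 0.0125 = 0.167 (stated 0.17).
- Specificity, n = 60: 0.1265 + 0.0083 = 0.135 (stated as at most 0.14).
- AUC at 0.5: 0.116 by Hanley-McNeil, 0.113 by the Obuchowski binormal variance (stated 0.12).
- Spearman at rho = 0, Fisher z with SE 1/√97: width 0.393 (stated 0.39).

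All four reproduce. None concerns additional sites, for which the plan states no figure.

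**3. Illustration A: inflation under assumed rates.** Let d be the share of patients with a true additional cancer that CEDM detects, and f the share of the remaining patients with a benign finding. Neither is in the documents. Assume d = 0.10 × 0.90 = 0.09. If every flagged patient is counted, reported frequency = d + (1 − d)·f and PPV = d / reported.

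- f = 0.05: 0.09 + 0.91 × 0.05 = 0.136; PPV 0.66.
- f = 0.10: 0.09 + 0.91 × 0.10 = 0.181; PPV 0.50.
- f = 0.20: 0.09 + 0.91 × 0.20 = 0.272; PPV 0.33.

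**4. Illustration B: what a confirmed count would show.** Suppose 20 of 100 patients are flagged (also an assumption). The Wilson 95% interval is [p + z²/2n ± z·√(p(1−p)/n + z²/4n²)] / (1 + z²/n). The unconfirmed count reports 20% (13.3% to 28.9%).

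| PPV | Confirmed (95% CI) | False-positive patients |
|---|---|---|
| 0.3 | 6% (2.8% to 12.5%) | 14 |
| 0.5 | 10% (5.5% to 17.4%) | 10 |
| 0.7 | 14% (8.5% to 22.1%) | 6 |
| 0.9 | 18% (11.7% to 26.7%) | 2 |

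Over the same PPV range, 10 flagged patients would include 1 to 7 false positives, and 30 flagged would include 3 to 21. The same 20% report fits every row, and the planned data would not show which row applies.

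**5. Would surgical pathology alone settle it?** No. Baseline CEDM precedes neoadjuvant therapy, and the plan expects pCR in 40% of patients. A true additional cancer at baseline may be gone by surgery, and a contralateral site may never be resected. Negative surgical tissue after therapy therefore does not show that a baseline finding was benign.

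**The case against.** The strongest reply is that the documents are silent on confirmation rather than wrong. A reader might infer that the plan orders every CEDM finding to be counted as cancer. It does not: section 5.2 speaks of findings, while the endpoint speaks of disease and section 8.3 of cancer. A careful team could drop a finding shown to be benign. That stands, and it is why the point says false positives can be counted, not that they will be. But nothing requires the team to drop them or says how to treat sites without tissue.

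A reader might also infer that the count can only favor CEDM over mammography. The documents do not support that. The endpoint in section 2.4.2 involves no comparison, and the one in section 8.3 can include ultrasound and MRI. Other modalities also mislead: Table 1 notes false positives on whole-breast ultrasound, and section 1.2 says mammographic microcalcifications do not correlate with viable tumor.

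Section 1.3 reports that CEDM raises sensitivity over mammography and ultrasound without losing specificity. That rests on earlier detection studies, and an unconfirmed count could not test it here.

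Finally, this is a descriptive secondary endpoint in a study that section 8.2 calls exploratory, with no test or decision rule attached. That limits the priority of the point but not its validity.

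**Conclusion.** The point holds as a gap in endpoint definition and analysis. As written, the plan cannot separate added cancer yield from false-positive findings, either for CEDM alone or between modalities. The primary endpoint is unaffected, and no stated number is wrong.

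The size is unknown. Under the assumptions of illustration A, the reported frequency is 1.5 to 3 times the true 9% (0.136/0.09 to 0.272/0.09). If the PPV were 0.9, the distortion would be small. A reader might take one of these figures as an estimate for this trial, but the documents give no rate of additional sites and no PPV. The illustrations also count every benign finding as disease, which is the worst case if some are removed after work-up.

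Nor should a reader assume that a confirming result will usually exist, since section 5.2 requires no tissue diagnosis. The change is inexpensive and worth making.

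**What to change.** In sections 2.4.2 and 8.3, classify each additional site, for each modality, using only tissue obtained under standard of care:

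- **Confirmed malignant:** malignant on tissue from that site, by biopsy or surgical pathology.
- **Confirmed benign:** benign on tissue taken from that site before treatment began.
- **Unverified:** never sampled, or a baseline site not biopsied before therapy and negative at post-therapy surgery.

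Compare modalities on confirmed malignant sites. Report the unverified count and the PPV among verified sites with 95% confidence intervals, allowing for several sites in one patient.

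The cost is a set of per-site case report form fields (site, modality, timepoint, tissue result) and the work of matching sites to pathology from records already followed under section 5.3. No procedure is added.

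There are downsides. The reported yield will be lower, and some sites will stay unverified. The PPV describes only worked-up sites and may run high, because malignancy can be confirmed before or after therapy but benign status only before it. At this sample size it will also be imprecise: 10 confirmed of 20 verified would give 50% (29.9% to 70.1%). Reporting the unverified count beside it lets readers judge how far it could move.

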## **6.2 Safety/tolerability**

Analyses will be performed for all patients having undergone at least one baseline and one mid or post therapy CEDM. We will perform standard of care pre and post CEDM monitoring in the immediate post CEDM phase, record and grade any reactions.

We will also ask patients to fill out a survey regarding their comfort level with **CEDM (APPENDIX B)** before their surgery.

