**APPENDIX B. CEDM PATIENT SURVEY/QUESTIONNAIRE**

***Comfort level and tolerance***

A. Please rate your comfort level during Breast MRI (please leave blank if not performed)	Extremely Comfortable 5	Relatively Comfortable 4	Neither comfortable Nor Uncomfortable 3	Somewhat Uncomfortable 2	Extremely Uncomfortable 1
B. Please rate your comfort level during Contrast-enhanced Mammography	Extremely Comfortable 5 1	Relatively Comfortable 4	Neither comfortable Nor Uncomfortable 3	Somewhat Uncomfortable 2	Extremely Uncomfortable

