***Disease Monitoring Preference- Please only respond if you also underwent breast MRI***

	Extremely Likely 5	Relatively Likely 4	Neither Likely Nor Unlikely 3	Somewhat Unlikely 2	Extremely Unlikely 1
G. Assuming they are equally accurate, how likely are you to choose contrast enhanced mammography over breast MRI as test of choice to measure your response ?					
H. How likely are you to choose contrast enhanced mammography over breast MRI for your annual routine screening in the future ?	Extremely Likely 5	Relatively Likely 4	Neither Likely Nor Unlikely 3	Somewhat Unlikely 2	Extremely Unlikely 1

Other Comments:

Appendix C. AJCC 8th edition pre- and post neoadjuvant therapy staging (see attached file).

612

American Joint Committee on Cancer • 2017

associated with significantly improved disease-free and overall survival for individual patients. A recent meta-analysis confirmed the reproducible prognostic value of pCR.

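### The timing objective is about residual disease extent, but its only endpoint is AUC, which does not show how well each delay sizes residual tumour

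*Combined protocol and SAP*

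**What the plan says.** Section 2.3 sets two exploratory aims. The timing aim is "To determine the optimal post neoadjuvant therapy CEDM timing which helps demonstrate the residual disease extent". The preference aim, 2.3.2, is "To identify any patient preference differences between CEDM and breast MRI". The endpoint entry for both, 2.4.3, reads "AUC of CEDM using varying time points for CEDM, survey scores for patient experience with CEDM". Section 8.1 restates the timing aim as performance in predicting pathologic response, so extent drops out.

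The related measurements and analyses are these:

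- **6.1.3:** pre-surgery CEDM lesion size is measured at 90-120 seconds, 5 minutes and 10 minutes. The largest single focus of enhancement is also recorded.
- **6.3:** pathologic size is ypT, the largest continuous focus of residual invasive cancer, without intervening fibrosis.
- **2.4.1:** AUC is taken against metrics that include pCR and RCB class.
- **8.3:** ROC analysis for CEDM and mammography, ICC between CEDM and mammography, and Spearman correlation of imaging size with pathologic size. None is specified by delay.

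On the survey, section 5.2 says "Survey of patient experience with CEDM and other pre-operative imaging such as MRI will be collected after CEDM is performed", while 6.2 describes only comfort with CEDM. Appendix B pairs MRI and CEDM ratings (A/B, C/D, E/F) and adds two direct preference items, G and H, for patients who also had MRI. Section 8.3 gives no survey analysis.

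**The concern.** Showing extent is a question of size: at a given delay, how close is the enhancing area to the tumour the pathologist measures? AUC answers a different question, namely whether patients in one response class rank above those in another. Two delays can have the same AUC and differ greatly in how well they size residual tumour. Results are meant to inform a larger multi-institutional study (8.2). A delay chosen on AUC alone could be carried forward although it systematically under- or over-sizes disease, and no planned analysis would reveal this.

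The term for time points in 2.4.3 is also undefined. It could mean the post-injection delays of 6.1.3 or the baseline, early and late imaging visits of section 4.0. The objective concerns post-therapy CEDM, which largely fixes the visit and favours the delay reading, but the endpoint does not say so.

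**Working it through.** **The plan's own figures.** Section 8.2 gives precision for the main analyses only. With N = 100 and 40% pCR (40 pCR, 60 not) these reproduce:

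- Sensitivity: 1.96 × √(0.25/40) + 1/80 = 0.155 + 0.0125 = 0.167 (stated 0.17).
- Specificity: 1.96 × √(0.25/60) + 1/120 = 0.127 + 0.008 = 0.135 (stated at most 0.14).
- AUC at 0.5, Hanley-McNeil: variance = [0.25 + (39 + 59)(1/3 - 1/4)]/2400 = 0.00351, so the half-width is 1.96 × 0.0592 = 0.116. The Obuchowski binormal form gives 0.113 (stated 0.12).
- Spearman at zero: 2 × tanh(1.96/√97) = 0.393 (stated 0.39).

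The figures are sound, but none concerns delay or the survey.

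**What AUC registers.** For residual tumour against pCR, AUC = P(X_res > X_pCR) + ½P(X_res = X_pCR), where X is CEDM size. Two facts follow.

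1. Multiplying every X by a constant c > 0 changes no ordering, so AUC is unchanged. This also holds for an AUC against RCB cut-points.
2. Exchanging sizes among patients within the residual-tumour group leaves the set of between-group pairs unchanged. An AUC for pCR is therefore unchanged even if CEDM size says nothing about pathologic size. An AUC against RCB cut-points would generally register this.

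**Illustration.** The documents give no lesion sizes, so these are assumptions. There are 60 patients with residual tumour, with lognormal pathologic size (median 15 mm, log-SD 0.6) and CEDM size with multiplicative error of log-SD 0.15. There are 40 pCR patients, each with a 40% chance of false enhancement (median 8 mm, log-SD 0.5). One simulated data set gave:

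| CEDM sizes | AUC for pCR | Spearman, residual group | Mean error (mm) | Mean absolute error (mm) |
|---|---|---|---|---|
| As generated | 0.909 | 0.95 | 0.05 | 1.6 |
| All halved | 0.909 | 0.95 | -7.7 | 7.7 |
| Permuted within residual group | 0.909 | -0.18 | 0.05 | 8.1 |

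Halving lowers the mean by 0.05 + 7.69 = 7.74 mm, so the mean CEDM size in the residual group is 15.48 mm. A milder 30% under-sizing would give a mean error of 0.05 - 0.3 × 15.48 = -4.6 mm, again with AUC 0.909. Spearman misses the scale error, and mean error misses the permutation. Bias and limits of agreement together would show both.

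**Precision of the added measure.** With n = 60, the 95% half-width for mean bias is 1.96/√60 = 0.25 SD of the differences. For each limit of agreement it is about 1.96 × √(1/60 + 1.96²/(2 × 59)) = 0.43 SD. That is adequate for a descriptive aim.

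**Survey.** Objective 2.3.2 is a CEDM-MRI difference, whereas 2.4.3 names CEDM scores alone. Appendix B supplies the rest: "Please rate your comfort level during Breast MRI (please leave blank if not performed" is matched by the CEDM comfort item, scan time and satisfaction are matched likewise, and G asks "how likely are you to choose contrast enhanced mammography over breast MRI as test of choice to measure your response". What is missing is the naming of these items as the endpoint. The number of patients with MRI is not stated. If 30, 50 or 100 had it (assumed), the maximum 95% half-width for a preference proportion, 1.96 × √(0.25/n), is 0.18, 0.14 or 0.10.

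**The case against.** The strongest defence is that AUC is relevant to timing. Section 2.4.1 takes it against RCB class as well as pCR, and RCB grades residual disease. The protocol's rationale for later imaging is visibility: contrast delivery may be delayed after chemotherapy (1.2), and longer delays may enhance more strongly (1.3). A delay that misses residual tumour will lower AUC. This stands. A reader might infer that AUC can say nothing about timing, and the documents do not support that. It speaks to whether a delay reveals residual disease, and through RCB coarsely to how much. It does not speak to sizing error.

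A size measure has limits of its own. Restricting it to residual tumour leaves false enhancement in pCR patients uncounted, and ypT is one focus, not overall extent in multifocal disease. Both are correct. They are reasons to keep AUC alongside and to compare like with like, not to omit sizing.

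On the survey, a reader might infer that only CEDM data are collected and that 2.3.2 is unanswerable. Section 5.2 and Appendix B show otherwise. A reader might also infer a biased contrast of all patients' CEDM scores with a subset's MRI scores, but no section plans one. Nor is there support for a lean toward CEDM in G and H. They name one direction, but the scale is balanced with a neutral midpoint, and G stipulates equal accuracy.

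Finally, these are exploratory endpoints in a descriptive study, and 8.3 allows further exploratory analyses as needed. That limits the severity. It does not make the stated endpoint match the stated objective.

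**Conclusion.** The timing mismatch holds. The objective is residual extent, the endpoint is AUC, and no planned analysis measures agreement of CEDM size with pathologic size at each delay. The change in AUC under uniform mis-sizing is exactly zero, whatever the factor. The millimetre figures (-4.6 for 30% under-sizing, -7.7 for halving) rest on the assumed size distribution and show the mechanism only. The conclusion assumes that time points in 2.4.3 means post-injection delays, which 6.1.3 supports but 2.4.3 does not state.

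The survey part is a wording gap: the data for a within-patient CEDM-MRI comparison are already planned. Severity is low overall, since the primary endpoint and the sample size statement are unaffected.

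**What to change.** **Timing, in 2.4.3 and 8.3**

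- State that time points means the post-injection delays in 6.1.3, and align the wording of 8.1 with the objective.
- For each delay (90-120 seconds, 5 minutes, 10 minutes), report the within-patient difference between CEDM size and pathologic size, as mean bias with limits of agreement, in patients with residual tumour. Enter a size of zero where residual tumour does not enhance.
- Use the largest single focus of enhancement against ypT, so that the two measures are comparable. Section 6.1.3 does not say that this focus is recorded at every delay, so the reading form should say so.
- Keep AUC by delay in all patients alongside it, so that false enhancement in pCR patients still counts.

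**Survey, in 2.4.3 and 8.3**

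- Name the within-patient differences B-A, D-C and F-E in patients who had both tests, plus items G and H, and report how many patients that is. The questionnaire needs no change.

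**Cost.** This takes a text amendment and a little more analysis. If the largest focus was not recorded at each delay, stored images would need re-measuring. The size measure excludes pCR patients. It covers about 60 of 100 at the assumed 40% pCR, or slightly fewer if some non-pCR patients are ypT0, as Appendix C allows when only intravascular or intralymphatic disease remains.
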